## **EARLY TERMINATION**

Any individual whose health or well-being may be threatened by continuation in this study will be discontinued by the investigator.

If a female subject becomes pregnant at any time during the study, she will be discontinued immediately. She will be asked to provide the investigator with medical updates throughout her pregnancy and on the final outcome of the pregnancy.

Any subject who chooses to discontinue the study, or is discontinued from the study by the investigator will be asked to return for a final visit to have some or all of the following procedures: assessment of adverse events and concomitant medications, questionnaires, pregnancy test, blood draw for complete blood count, and skin evaluation including PASI, sPGA, and BSA.

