## **ENDPOINTS:**

**Primary endpoint:** Proportion of patients achieving a score of “0-clear” or “1-almost clear” in the sPGA score after 16 weeks of treatment.

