## **RESEARCH DESIGN:**

This is an open-label study of a total of 40 subjects enrolled at 3 to 4 sites, with moderate-to-severe psoriasis who have previously failed treatment with an IL-17A agent. Subjects will receive brodalumab 210 mg via subcutaneous injection at weeks 0, 1, and 2, followed by 210 mg every 2 weeks; total study length is 16 weeks.

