### **Inclusion criteria:**

1. Male or female subject at least 18 years of age
2. Subject is able to provide written informed consent and comply with the requirements of this study protocol.
3. Have both a sPGA score of  $\geq 3$  and BSA  $\geq 5\%$  prior to randomization.

4. Subjects who are women of childbearing potential must have a negative urine pregnancy test at screening and must be practicing an adequate, medically acceptable method of birth control for at least 30 days before Day 0 and at least 6 months after the last study drug administration. Acceptable methods of birth control include intrauterine device (IUD); oral, transdermal, implanted or injected hormonal contraceptives (must have been initiated at least 1 month before entering the study); tubal ligation; abstinence and barrier methods with spermicide. Otherwise, if not of childbearing potential, subjects must: have a sterile or vasectomized partner; have had a hysterectomy, a bilateral oophorectomy or be clinically diagnosed infertile; or be in a menopausal state for at least a year.
5. Tuberculin purified protein derivative (PPD) or QuantiFERON TB-Gold test (QFT) negative at the time of screening, or if patient has a history of positive PPD or QuantiFERON, he/she has initiated or completed the appropriate prophylaxis.
6. Subject is judged to be in good general health as determined by the principal investigator based upon the results of medical history and laboratory profile.
7. Subject has previously failed treatment with an IL-17A agent, secukinumab or ixekizumab, (where available, defined as previous treatment with either drug for at least 3 months without achieving PASI-75 response or a 50% loss of original improvement).
8. Last administration of secukinumab or ixekizumab  $\geq$  28 days prior to Baseline.

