#### **STATISTICAL METHODS:**

Individual efficacy variables, the sum of those variables, and safety parameters will be analyzed separately. Subjects who discontinue prematurely because of inadequate response or because of adverse events will have their last results carried forward for purposes of analysis.

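### The early-termination text and the Schedule of Events disagree on skin scoring, and the carry-forward rule does not define the last result, so a lapsed responder who stops unscored could count as a Week 16 responder

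*Combined protocol and SAP*

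**What the plan says.** Three parts of the combined protocol and SAP bear on this.

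- **EARLY TERMINATION.** A subject who stops, or is stopped by the investigator, is asked back for a last visit "to have some or all of the following procedures". The list ends with "skin evaluation including PASI, sPGA, and BSA". No item on it is named as mandatory.
- **Appendix A, Schedule of Events.** Week 16 and early termination share one column, V6/ET. The sPGA, PASI and BSA rows are marked there as at every other visit, and no footnote makes them optional.
- **STATISTICAL METHODS.** The only rule for missing outcomes is: "Subjects who discontinue prematurely because of inadequate response or because of adverse events will have their last results carried forward for purposes of analysis". It does not say whether a termination score is the last result, or what happens when there is none.

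The primary endpoint is the proportion clear or almost clear "in the sPGA score after 16 weeks of treatment". RESEARCH DESIGN states: "This is an open-label study of a total of 40 subjects enrolled at 3 to 4 sites". There is no comparator. METHODS sets post-baseline skin scoring at Weeks 4, 8, 12 and 16.

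**The concern.** Carry-forward is only as good as the score it carries. If a subject stops because the skin has worsened and nobody scores the skin at exit, the value that stands for Week 16 comes from the previous monthly visit, before the worsening was recorded. If that value was sPGA 0 or 1, a treatment failure enters the analysis as a success.

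The pattern is plausible in this population. Inclusion criterion 7 admits subjects whose earlier IL-17A treatment worked and then lost half its benefit. The study is open label, so staff who know the treatment also decide which exit procedures to do. With a single arm, no control group carries the same error, and any misclassification goes straight into the reported proportion. PASI-75, PASI-90, PASI-100 and the 50% BSA improvement endpoint use the same visits and are open to the same error.

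**Working it through.** The plan states no dropout rate, target response rate or sample-size derivation, so there is no figure of its own to reproduce. The check has two parts.

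**1. Which score stands as the result**

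Take a subject who stops between scheduled visits. With all visits attended, the last scheduled score is up to about four weeks old; a longer gap needs a missed visit as well.

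- *Exit score taken and used.* The result reflects the skin at stopping, and the problem does not arise.
- *No exit score, stop for inadequate response, never reached sPGA 0 or 1.* The older score is a non-response, so the primary endpoint is unchanged.
- *No exit score, baseline score only.* Inclusion criterion 3 reads "Have both a sPGA score of" at least 3, so the subject is a non-responder. On PASI and BSA the improvement from baseline is zero, also a non-response.
- *No exit score, stop for inadequate response, sPGA 0 or 1 at the last scheduled visit and since lost.* The subject is counted as a Week 16 responder. This is the case that goes wrong.
- *No exit score, stop for an adverse event.* The older score may be better or worse than the skin at exit. A subject still improving would be understated.

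**2. Size**

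With N = 40, each misclassified subject adds 1/40 = 2.5 percentage points. For illustration, assume a true count of 20 responders (exact Clopper-Pearson 95% intervals):

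- 20/40 = 50.0% (33.8 to 66.2)
- one misclassified: 21/40 = 52.5% (36.1 to 68.5)
- two misclassified: 22/40 = 55.0% (38.5 to 70.7)

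The expected number of misclassified subjects is N × d × m × q, where

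- d = share of subjects stopping for inadequate response,
- m = share of those without an exit score,
- q = share of those whose last scheduled sPGA was 0 or 1, all taken to have lost it by exit.

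None of the three is in the documents. Assumed ranges are d = 5 to 20%, m = 25 to 100% and q = 10 to 50%:

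- low: 40 × 0.05 × 0.25 × 0.10 = 0.05 subject, about 0.1 point
- middle: 40 × 0.10 × 0.50 × 0.25 = 0.5 subject, 1.25 points
- d = 10%, m = 100%, q = 50%: 40 × 0.10 × 1.00 × 0.50 = 2 subjects, 5 points
- high: 40 × 0.20 × 1.00 × 0.50 = 4 subjects, 10 points

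If every attending subject is scored and that score is used, m = 0 for attenders and the error from this source is zero. A subject who does not attend still has only an older score unless the plan says otherwise.

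**The case against.** The strongest reply is that the schedule already requires the scores. Appendix A marks all three at V6/ET, and the loose phrase in EARLY TERMINATION may only cover items that do not apply to everyone, such as the pregnancy test. It would therefore be wrong to infer that skin scoring at termination is simply optional; the documents show a conflict. The conflict still stands. No passage says that the schedule prevails, and the two lists differ in other ways: EARLY TERMINATION names questionnaires and a blood count, while Appendix A has no questionnaire row and marks the blood count only at screening. A site cannot safely read the text as shorthand for the column, and one that omits scoring has followed the text.

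The second reply is that the error needs several things together: a stop for inadequate response, no exit score, a last scheduled sPGA of 0 or 1, and loss of that response before stopping. Someone clear or almost clear at the last visit is not an obvious candidate to stop for inadequate response. This is right, and it keeps the likely size small.

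The third is that a reader might infer that the error always favours the drug. That holds on the binary endpoints for stops due to inadequate response, where the exit state is taken to be a non-response. It does not hold for adverse-event stops.

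Finally, requiring a score cannot obtain one from a subject who does not return. That is why the plan also needs a rule for unscored stops.

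**Conclusion.** The point stands as an inconsistency between EARLY TERMINATION and Appendix A, joined to a carry-forward rule that does not define its key term. Together they allow a relapsed responder who stops unscored for inadequate response to be reported as a Week 16 success.

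The likely effect is modest: 0 to 2 such subjects, or 0 to 5 points on the primary proportion. That count is an assumption, since the documents give no dropout or response figures. A reader might reason that 2 to 6 stops would inflate the result by 5 to 15 points (2/40 and 6/40). The documents do not support this as an estimate. It is a ceiling, reached only if every one of those subjects had responded, relapsed and left without an exit score. The plan also states no success threshold, so no decision can be shown to change.

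The correction is still worth making before enrolment, because an exit score that was not taken cannot be recovered later.

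**What to change.** **EARLY TERMINATION:** require sPGA, PASI and BSA for every subject who attends the termination visit, in line with Appendix A. The other items can stay at the site's discretion.

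**STATISTICAL METHODS:**

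- State that the early-termination score is the last result.
- Count a subject who stops for inadequate response or an adverse event and has no exit score as a non-responder on the sPGA, PASI and BSA response endpoints.
- Report carry-forward of the older score as a sensitivity analysis.

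**Cost:** a few sentences, and no assessment beyond those already in Appendix A. The reported response proportion may be slightly lower. A subject who stops for an adverse event while still responding, and is not scored, would count as a non-responder; the sensitivity analysis shows how much that matters. One limit remains: an adverse-event stop with an early exit score of 0 or 1 would still be carried forward as a Week 16 responder. That belongs to the wider choice of carry-forward and is not settled here.

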## **INVESTIGATIONAL DRUG SUPPLY**

In this open-label study, Brodalumab will be provided by Valeant Pharmaceuticals as 210 mg brodalumab pre-filled syringes. Each site will be provided with a supply of brodalumab 210 mg for up to 15 subjects.

All study medication will be shipped to and stored by a REMS certified pharmacy in a secure cool area between 2-8°C (under refrigeration). Study drug will be dispensed to subjects at each visit, and any unused study drug will be kept at the study site. Subjects will be given a cooler to transport medication home, and instructed to keep the medication refrigerated. The number of missed doses will be documented for each subject. Each investigative site will account for all study drug dispensed and stored during the study.

### **LABORATORY SPECIMEN**

All blood and urine samples will be processed through the investigative's site local lab.

### **INSTITUTIONAL REVIEW BOARD**

Prior to beginning this study, approval for all study related documents (protocol, consent form, advertising) will be obtained from the investigative site's IRB.

## Appendix A

### Schedule of Events

	Screening	Baseline/Randomization	Treatment Phase			
	V1	V2	V3	V4	V5	V6/ET
Visit number	V1	V2	V3	V4	V5	V6/ET
Weeks since randomization	-4	0	w4	w8	w12	w16
Informed Consent	x					
Patient-Prescriber Agreement Form		x				
Medical History	x					
Demographics	x					
Inclusion/Exclusion	x	x				
Concomitant Medications	x	x	x	x	x	x
Adverse Events		x	x	x	x	x
Administer IP		x	x	x	x	
Dispense IP		x	x	x	x	
Clinical Efficacy						
sPGA	x	x	x	x	x	x
PASI	x	x	x	x	x	x
BSA	x	x	x	x	x	x
Photographs of target lesion(s) 		x	x	x	x	x
Laboratory Tests						
Quantiferon Gold/PPD (if not done in past 8 months)	x					
Urine Pregnancy (Females of child bearing potential)	x	x	x	x	x	x
Complete Blood Count w/ differential (if not performed in past 4 months)	x					

1 – **Photographs of at least one target lesion should be taken at baseline and then again at every visit thereafter.**  
**The same target lesion is to be photographed at each visit according to the site's SOPs.**

## Appendix B

### Psoriasis Area and Severity Index (PASI):

PASI	Head	Trunk	Upper Limbs	Lower Limbs	Symptom Score
Erythema (E)					0 = None 1 = Slight 2 = Moderate 3 = Severe 4 = Very Severe
Infiltration (I)					
Desquamation (D)					
Sum = E + I + D					
Area Score					0 = none 1 = <10% 2 = 10-29% 3 = 30-49% 4 = 50-69% 5 = 70-89% 6 = 90-100%
Sum x Area					
x	x 0.1	x 0.3	x 0.2	x 0.4	
Total	+	+	+	=	

## Appendix C

### Static Physician Global Assessment (sPGA)

sPGA	0	1	2	3	4
Induration (I) Averaged over all lesions	no evidence of plaque elevation	minimal plaque elevation (0.25 mm)	mild plaque elevation (0.5 mm)	moderate plaque elevation (0.75 mm)	severe plaque elevation (> 1 mm)
Erythema (E) Averaged over all lesions	no erythema, hyperpigmentation may be present	faint erythema	light red coloration	moderate red coloration	bright red coloration
Scaling (S) Averaged over all lesions	no evidence of scaling	minimal; occasional fine scale over <5% of lesion	mild; fine scale dominates	moderate; coarse scale predominates	severe; thick scale predominates

Add I + E + S = \_\_\_\_\_ / 3 = \_\_\_\_\_ (Total Average)
